Study protocol

Routine versus selective protamine administration to reduce bleeding in transcatheter aortic valve implantation (ACE-PROTAVI)

Melbourne, 10 March 2021

Protocol Synopsis

Title	Routine versus selective protamine administration to reduce bleeding in transcatheter aortic valve implantation
Acronym	ACE-PROTAVI
Principal	[name]
Investigators	[name]
J	The Heart Centre, The Alfred Hospital, Melbourne Australia
	Department of Cardiology, Epworth Healthcare, Melbourne Australia
Co-	[name]
investigators	[name]
	[name]
	[name]
	[name]
	[name]
Study	Routine administration of protamine reduces vascular and bleeding
Hypothesis	complications in TAVI patients, compared with selective administration,
	therefore improving clinical outcomes (reduced morbidity and mortality),
	but also reducing healthcare costs (by reducing length of stay, additional
 	vascular interventions, and improving post-procedural recovery).
Study Design	Randomised controlled trial in which patients are randomised between
	routine protamine administration at the end of the procedure, or selective
Ctudy	Use of protamine if clinical scenario requires it.
Sludy	Patients with symptomatic severe aonic stenosis of regulgitation who are
population	surgical risk, frailty, and other clinically relevant factors
Primary	Time to haemostasis: elansed time after sheath removal and first observed
obiective	and confirmed arterial haemostasis.
Secondary	- Composite rate of all-cause mortality, major and minor bleeding
objectives	and vascular complications according to VARC-2 criteria at 30-day
•	follow-up
	- Each individual component of first secondary endpoint.
	 Need for transfusion for (access-site related) bleeding
	 Hematoma size by vascular ultrasound
	- Myocardial infarction
	- Stroke
	- Length of stay
	- Rate of delayed haemostasis failure
Inclusion	Patients undergoing elective trans-temoral TAVI for severe aortic valve
	stenosis with any commercially available transcatheter heart valve.
EXCIUSION oritoria	- Documented protamine allergy or anaphylaxis
criteria	- Recent PUI (< 3 months)
	- Fianneu alterial access via surgical cut-down
Intervention	Routine protamine administration at the time of sheath removal after
	successful denloyment of THV

Table of contents

Protocol Synopsis	2
Table of contents	3
1 Introduction and rationale	6
1.1 Lay summary	6
1.2 Background	6
1.3 Study hypothesis and aims	7
1.4 Trial registration	8
2 Objectives	8
2.1 Primary objective	8

1.1 Lay summary

In patients with diseased aortic valves, catheter-based replacement of the sick valve (TAVI) is a less invasive alternative for surgical valve replacement. TAVI has become the procedure of first choice in patients with increased operative risk. Because the valve is implanted through a catheter from the groin, there is no need for open heart surgery and recovery is much quicker. However, there remains a risk of major or life-threatening bleeding from the access site, especially because patients require blood-thinners (heparin) during the valve implantation. At the end of the procedure, when blood-thinners are no longer required, the effect of heparin can be reversed by protamine injection, but routine use of protamine has not been tested in TAVI patients in a randomised trial. In this study we will evaluate if routine use of protamine reduces the risk of major bleeding and improves outcomes for patients who underwent TAVI. We will compare safety and effectiveness of routine use of protamine in a randomised controlled trial and will compare outcomes after 30 days. The results of this study will help to improve the safety of the TAVI procedure and its outcomes for patient (reduced morbidity and mortality) and society (reduced demand on constrained economic resources).

1.2 Background

Degenerative aortic valve disease is the most prevalent valvular heart disease in the elderly. If left untreated after the appearance of symptoms, expected mortality after two years is almost 50%.¹ In the last 10-15 years, transcatheter aortic valve replacement (TAVI) matured into a less invasive alternative for surgical valve replacement, and landmark randomised clinical trials have demonstrated that TAVI is non-inferior (and maybe superior) to surgical valve replacement across the entire risk spectrum in elderly patients with degenerated tricuspid aortic valve stenosis.^{2–8} Despite its successes, TAVI is not a procedure free from complications. Vascular

complications, especially those related to the access site, are one of the most feared and frequent procedure-related complications. Life-threatening or major bleeding Major or life-threatening bleeding not only leads to increased length of stay and increased strain on healthcare resources, but more importantly, they are associated with increased morbidity and mortality. Therefore, prevention of bleeding and selection of the appropriate treatment for vascular complications play a pivotal role to further improve patient outcomes after TAVI.

During the TAVI procedure, heparin anticoagulation is recommended before introduction of the guiding sheath, while maintaining an activated clotting time of >300 s. This recommendation by the American College of Cardiology Foundation/American Association for Thoracic Surgery/Society for Cardiovascular Angiography and Interventions/Society of Thoracic Surgeons (ACCF/AATS/SCAI/STS) expert consensus document on TAVI is based on expert consensus rather than on evidence from RCTs.⁹ Heparin reversal by administration of protamine, prior to removal of the sheath and closure of the arteriotomy site, can be considered. However, daily practice varies widely among centres and even operators, from routine protamine administration to almost none or selective administration (in patients at high risk of bleeding).

Although protamine is routinely used in cardiac surgery, the data regarding its safety and efficacy in prevention of bleeding complications in TAVI is scarce. One recent observational study demonstrated in 873 patients that routine administration of protamine significantly reduced bleeding and vascular complications, compared with no protamine (4.1% vs 11.8%), and that there was no increase in ischemic events such as stroke and myocardial infarction (1.8% vs 3.6%). However, the study was performed in a non-randomised, non-matched population with a high risk for selection bias, especially in patients not receiving protamine.¹⁰

1.3 Study hypothesis and aims

Major bleeding and vascular complications after TAVI are associated with increased morbidity and mortality, and increased demand on restrained healthcare resources. Our hypothesis is that routine protamine administration at the conclusion of the TAVI procedure reduces the risk of major bleeding and vascular complications, without increasing the risk of ischemic events. Our study aims to improve outcomes after TAVI, by demonstrating the efficacy and safety of routine protamine administration in a randomized controlled setting.

1.4 Trial registration

The trial will be registered on Clinicaltrials.gov.

2 Objectives

2.1 Primary objective

The primary objectives of this study are to determine if routine protamine administration, compared with selective protamine administration, reduces the risk of procedural haemostasis failure and reduces the time to haemostasis (TTH): elapsed time after sheath removal and first observed and confirmed arterial haemostasis.

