4.4 Sample size

Sample size calculation for a 25% reduction of baseline 13 ± 10 min of TTH after sheath removal, with >80% power and a 2-sided a of 0.05 leads, and a drop-out of 15% to a minimum of 400 enrolled patients.

The baseline TTH is based on several published studies: a randomised trial comparing proglide and prostar devices after large-bore arteriotomy (mean TTH was 9.8±17 minutes after ProGlide and 13±19 minutes after ProStar)¹¹ and a prospective registry of the Manta device (mean TTH 2.4 minutes)¹².

5 Treatment of subjects

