8.6.1. Monitoring for effectiveness

The DSMB is responsible for monitoring greater than expected efficacy, using adjudicated endpoints events. The DSMB will undertake an interim analysis after 100 patients have been

enrolled in each arm of the study. The study will be stopped if there is a significant difference in the primary outcome measure between the two arms (p<0.001) at the interim analysis.

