13.1 Primary outcome

The primary endpoint is described in chapter 2.1. Procedural haemostasis failure will be defined as failure to achieve haemostasis at the arteriotomy site leading to alternative treatment (e.g. fem-stop device, or adjunctive endovascular ballooning/stenting). Time to haemostasis will be measured in the time (minutes) elapsed after large sheath removal and first observed and confirmed arterial haemostasis.

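### The protocol contradicts itself on whether the primary endpoint is time to haemostasis alone or also procedural haemostasis failure, and does not say what counts as success

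*Protocol*

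**What the plan says.** The places that speak to the primary endpoint do not match.

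- **Section 2.1** uses the plural: "The primary objectives of this study are to determine if routine protamine administration", compared with selective administration, "reduces the risk of procedural haemostasis failure and reduces the time to haemostasis (TTH"). That makes two objectives joined by *and*.
- **Section 13.1** uses the singular and then opens with the other endpoint: "The primary endpoint is described in chapter 2.1. Procedural haemostasis failure will be defined as failure to achieve haemostasis at the arteriotomy site". A definition of TTH follows.
- **Section 7.1** sends the reader to 2.1 and chapter 13 for the endpoints, so the two-endpoint text is the one in force for conduct of the trial.
- **The synopsis** has one primary objective: "Time to haemostasis: elansed time after sheath removal and first observed" (the misspelling comes from reading the PDF). Procedural haemostasis failure appears there neither as primary nor as secondary. The only failure endpoint in the synopsis is delayed failure, a secondary, which section 13.2.12 defines separately.
- **Section 4.4** rests on TTH alone: "Sample size calculation for a 25% reduction of baseline 13 ± 10 min of TTH after sheath removal". It uses one two-sided alpha of 0.05, asks for more than 80% power, allows 15% for drop-out and arrives at 400 patients or more.
- **Section 8.6.1** fixes the interim rule: "The study will be stopped if there is a significant difference in the primary outcome measure between the two arms (p<0.001"). It does not say which endpoint is meant.

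**The concern.** A reader of the synopsis and section 4.4 would plan one confirmatory test at 5%. A reader of sections 2.1 and 13.1 would plan two. The protocol does not rank the endpoints or say whether one success is enough, and each answer has a different consequence for error rate or power.

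The interim rule is directly exposed. At 100 patients per arm one endpoint could cross p<0.001 while the other does not. Section 8.6.1 says that the trial will then be stopped, or will not, depending on a name that it does not give. If the matter is settled only after results are known, the main claim of the trial can be questioned whichever way it is settled.

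**Working it through.** **Inputs.** Section 4.4 gives a baseline mean of 13 min, SD 10 min, 25% reduction, two-sided alpha 0.05, power above 80%, drop-out 15% and at least 400 enrolled. Allocation of 1:1 is assumed; it is not stated as a ratio, but the interim look is set at 100 in each arm.

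**1. Reproduce the plan's figure for TTH alone.** Difference = 0.25 × 13 = 3.25 min. Per arm, n = 2 × (z for alpha + z for power)² × (10/3.25)², with (10/3.25)² = 9.467.

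- 80% power: 2 × (1.960 + 0.842)² × 9.467 gives 149 per arm, 298 evaluable; 298/0.85 gives 351 enrolled.
- 85% power: 2 × (1.960 + 1.036)² × 9.467 gives 171 per arm, 342 evaluable; 342/0.85 gives 403 enrolled.
- 400 enrolled: 400 × 0.85 = 340 evaluable, 170 per arm. Standard error = 10 × √(2/170) = 1.085; 3.25/1.085 = 2.996; 2.996 − 1.960 = 1.036; power 85.0%.

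So 400 agrees with power above 80% for TTH as the only primary.

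**2. Either endpoint suffices, each at 0.05.** If the test statistics are independent, the chance of at least one false positive is 1 − 0.95² = 9.75%. For correlated statistics (bivariate normal):

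| Correlation | At least one false positive | Both false positive |
|---|---|---|
| 0 | 9.75% | 0.25% |
| 0.3 | 9.5% | 0.5% |
| 0.5 | 9.1% | 0.9% |
| 0.7 | 8.3% | 1.7% |
| 0.9 | 7.0% | 3.0% |

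The protocol gives no correlation, so the range is what can be stated. The two endpoints describe closure of the same arteriotomy, so independence is the extreme case.

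**3. Either suffices, alpha split to 0.025 each.** The critical value is 2.241. TTH power with 170 per arm: 2.996 − 2.241 = 0.755, which gives 77.5% (77.2% from the t distribution). To recover 80% for TTH takes 180 per arm, 360 evaluable, and 360/0.85 gives 424 enrolled. Under Holm, TTH power lies between 77.5% and 85%, because TTH is tested at 0.05 when failure is significant at 0.025.

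**4. Both required, each at 0.05.** The false-positive rate never exceeds 5%, and no split is needed. Power for joint success cannot exceed that of the weaker endpoint. If the two are independent, joint power of 80% would need failure power of 0.80/0.85 = 94%. The protocol gives no procedural failure rate, so actual power cannot be computed. As an illustration only, assume control rates of 5% to 15%, halved by treatment. Failure power with 170 per arm is then 23% to 59%, and joint power under independence is about 19% to 50%.

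**5. Interim look.** A test at 0.001 adds at most 0.001 per endpoint to the error rate. The problem there is the missing name, not the alpha.

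**The case against.** Three points on the other side carry weight.

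First, a reader might infer that the trial does not hold its 5% error rate. The documents do not support that as a flat statement. It follows only if a win on either endpoint at 0.05 counts, and no section says so. Section 2.1 joins the objectives with *and*, and 13.1 speaks of one primary endpoint. If both must succeed, 5% is held.

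Second, a testing order or alpha split is commonly left to the SAP, which is not shown. Its absence here is therefore no fault. That answers the multiplicity question but not the contradiction. The choice of primary endpoint belongs in the protocol, and a SAP cannot make the synopsis, 2.1, 4.4 and 13.1 say the same thing. The stopping rule is likewise written into this protocol.

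Third, a reader might infer that 400 is too few, or that procedural failure is shown to be underpowered. Neither is established. The figure of 400 reproduces for TTH. For failure there is no rate to work from. The 11.8% in section 1.2 concerns bleeding and vascular complications without protamine in an observational study, which is a different endpoint and a different comparator.

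The synopsis was also poorly read from the PDF, and at least one of its rows lost words. Its TTH entry reads as complete, however, and section 4.4 independently treats TTH as the only endpoint that sizes the trial.

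**Conclusion.** The contradiction stands and needs correcting before unblinding: two primary objectives in 2.1, one in the synopsis and the sample size, and one unnamed measure in the interim rule.

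Its size depends on the rule that the investigators intend. With success on either endpoint at 0.05, the error rate is about 7.0% to 9.75% for correlations from 0.9 to 0. With 0.025 each, TTH power is about 77% instead of 85%, assuming SD 10, 1:1 allocation and 170 evaluable per arm. With both required, the error rate is sound, but the power stated in 4.4 is not the power of the trial, and the true figure cannot be derived from the protocol. Only TTH as the single primary keeps the stated alpha, the stated power and the 400 patients all true, and that is the reading that 2.1 contradicts.

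**What to change.** Preferred: make TTH the single primary endpoint at two-sided 0.05 in 2.1 and 13.1, in line with the synopsis and 4.4. Move procedural haemostasis failure to first key secondary, tested at 0.05 only if TTH is significant, and add it to the secondary lists in 2.2 and the synopsis, where it does not now appear. In 8.6.1, name TTH as the endpoint of the p<0.001 rule.

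If the investigators prefer to keep both as primary, they should change the synopsis to match 2.1. They should state whether success means either endpoint (with Holm or 0.025 each) or both, restate the power with an explicit assumption for the failure rate, and say which endpoint triggers the interim stop.

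The preferred route costs wording only and leaves 400 unchanged. Its price is that haemostasis failure cannot be claimed on its own when TTH is null. Keeping both with a split at 0.025 would need about 424 enrolled to hold 80% power for TTH.

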2.2 Secondary objective

The secondary objectives of this study are to determine if reversal of heparin by routine administration of protamine, compared with selective protamine administration reduces:

- the risk of the composite of all-cause death, major and minor bleeding complications, major and minor vascular complications after 30 days.
- 2) the risk of each individual component of the first secondary outcome
- 3) the need for transfusion for access-site related bleeding
- 4) the hematoma size on vascular ultrasound 3-48h after procedure

- 5) the risk of myocardial infarction
- 6) the risk of stroke
- 7) length of stay post-procedure
- 8) the rate of delayed haemostasis failure.

3 Study design

ACE-PROTAVI is a randomised, double blind placebo-controlled trial in patients undergoing

TAVI, comparing routine protamine administration versus selective protamine administration.

3.1 Proposed timeline of trial

The expected timeline and study milestones are shown in the Gantt chart below.

Study timeline (months)

4 Study population

4.1 Population

The study population will consist of patients with symptomatic severe aortic stenosis or regurgitation that are accepted in multidisciplinary heart team for TAVI, based on predicted surgical risk, frailty, and other clinically relevant factors.

Patients will be recruited from the Alfred Hospital, Cabrini Hospital and Epworth Hospital, all located in Melbourne, Australia.

4.2 Inclusion Criteria

Participants eligible for inclusion in this study are:

- aged > 18 years,
- undergoing elective trans-femoral TAVI with any commercially available transcatheter heart valve.

4.3 Exclusion Criteria

Participants not eligible for inclusion in this study are:

- Documented protamine allergy or anaphylaxis
- Recent PCI (< 3 months)
- Planned arterial access via surgical cut-down
- Pregnancy

4.4 Sample size

Sample size calculation for a 25% reduction of baseline 13 ± 10 min of TTH after sheath removal, with >80% power and a 2-sided a of 0.05 leads, and a drop-out of 15% to a minimum of 400 enrolled patients.

The baseline TTH is based on several published studies: a randomised trial comparing proglide and prostar devices after large-bore arteriotomy (mean TTH was 9.8±17 minutes after ProGlide and 13±19 minutes after ProStar)¹¹ and a prospective registry of the Manta device (mean TTH 2.4 minutes)¹².

5 Treatment of subjects

5.1 Investigational product/treatment

The investigational treatment will be one dose of protamine IV in a 0.6-1.0 ratio of 1mg per 100IU of heparin.

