6.4 Description of justification of route of administration and dosage

A comprehensive review on dosing of protamine suggests that protamine administration based on the initial heparin dose should target a ratio below 1:1 in order to prevent protamine-related coagulopathy and bleeding, but the exact ratio is not elaborated and may vary between 0.6 and 1.0 based on the initial heparin dose.²¹

In this study the final dosage of protamine will be at the operator's discretion but should not exceed total heparin dose.

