6.5 Preparation and labelling of investigational medicinal product

Two 10cc syringes, one with protamine (10mg/mL) and one placebo (10mL NaCl 0.9%) will be prepared by either the anaesthetics team or the nursing staff. Dependent on outcome of randomisation, one syringe will be labelled with 'A' and contains protamine, and the other will be labelled 'B' and contains placebo, or vice versa. This will be documented, and primary operators will be blinded to the true contents of syringe A and B. (See also 7.3)

7 Methods

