7.2 Randomisation, blinding and treatment allocation

Randomisation forms will be generated by computer-generated code, numbered, and sealed in opaque envelopes, that conceals the treatment designation. Stickers with 'A' and 'B' will also be provided in the envelope.

For patients randomised to protamine syringe A will contain 100mg (10mg/mL) protaminesulphate. Syringe B will contain 10mL 0.9% NaCl. For patients randomised to placebo, syringe A will contain 10mL 0.9% NaCl, and syringe B will contain 100mg (10mg/mL) protaminesulphate.

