7.3 Study procedures

The patient will be consented for the study prior to the TAVI procedure. After successful deployment of the THV, the patient will be randomised, as described in paragraph 7.2.

Prior to removal of the large sheath, ACT will be assessed. Then syringe A will be injected and sheath-removal/arteriotomy closure per operator's discretion will be performed. If haemostasis is achieved, time between sheath removal and confirmed arterial haemostasis will be recorded.

If after 10 minutes no haemostasis is achieved, syringe B may be injected per operator's request. This preserves the blinding of primary operators but ensures if ongoing bleeding issues that protamine is injected to improve haemostasis (as would in routine management). The need for syringe B will be documented on the study registration form. A sticker on arterial access-site dressing will be applied, with a notification if compression on the ward is required, so delayed haemostasis failure can be documented. Femoral ultrasound will be performed 3-48h afterwards

to assess haematoma size and vascular complications. Time to discharge will be documented. Any occurrence of secondary endpoints during in-hospital stay will be documented.

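### Sections 5.1, 6.4, 6.5, 7.2 and 7.3 give protamine dosing instructions that do not agree, and none says which governs

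*Protocol*

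**What the plan says.** The protocol addresses the amount of protamine in four places.

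- **Section 5.1** gives "one dose of protamine IV in a 0.6-1.0 ratio of 1mg per 100IU of heparin". This has a lower and an upper limit. It does not say whether heparin means the initial or the total dose.
- **Section 6.4** cites a review under which the ratio "may vary between 0.6 and 1.0 based on the initial heparin dose". It then says that "the final dosage of protamine will be at the operator's discretion but should not exceed total heparin dose". This has an upper limit only, and its basis is total heparin.
- **Sections 6.5 and 7.2** fix the syringe contents: "For patients randomised to protamine syringe A will contain 100mg (10mg/mL) protaminesulphate". In the placebo arm the protamine is in the other syringe: "syringe B will contain 100mg (10mg/mL) protaminesulphate". The content is not scaled to heparin.
- **Section 7.3** gives the administration step: "Then syringe A will be injected". There is no step that calculates a volume, and no statement that part of a syringe may be given. Syringe B may follow at the operator's request if haemostasis has not been reached after 10 minutes, again with no volume.

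**The concern.** Staff who follow one section can breach another on the dose of the trial drug. The protocol's own text makes this more than a matter of style: 6.4 explains that a ratio below 1:1 is intended to avoid coagulopathy and bleeding caused by protamine itself, and 6.2 describes anticoagulant effects, some of them linked to higher doses. Time to haemostasis and procedural haemostasis failure are the primary outcomes in 2.1, and bleeding enters the first secondary outcome in 2.2. An inconsistent dose instruction therefore bears both on patient safety and on what the comparison of arms measures.

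The comparator is affected too, because the protamine available to placebo patients in syringe B is prepared and injected under the same instructions.

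**Working it through.** **Inputs**

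- Ratio limits: 0.6 and 1.0 mg protamine per 100 IU heparin (5.1).
- Cap: protamine not above total heparin (6.4), read here as 1.0 mg per 100 IU of total heparin.
- Syringe content: 10 mL × 10 mg/mL = 100 mg, which agrees with the figure in 7.2.
- Heparin dose: not given anywhere in the protocol. Section 1.2 mentions only an ACT above 300 s. The range 5,000 to 20,000 IU below is assumed for illustration.

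**Step 1. When does a whole syringe fit the ratio?**

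Heparin (IU) = 100 × protamine (mg) / ratio.

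- Ratio 1.0: 100 × 100 / 1.0 = 10,000 IU.
- Ratio 0.6: 100 × 100 / 0.6 = 16,667 IU.

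These two thresholds need no assumed heparin dose.

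**Step 2. Illustrative heparin doses**

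Range in mg = 0.6 × IU / 100 to 1.0 × IU / 100. Ratio of a full syringe = 100 / (IU / 100).

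| Heparin (assumed, IU) | 5.1 range (mg) | Ratio if 100 mg is given | Against 5.1 | Against 6.4 cap |
|---|---|---|---|---|
| 5,000 | 30–50 | 2.00 | above | exceeds |
| 7,000 | 42–70 | 1.43 | above | exceeds |
| 8,000 | 48–80 | 1.25 | above | exceeds |
| 10,000 | 60–100 | 1.00 | within | meets |
| 12,000 | 72–120 | 0.83 | within | meets |
| 15,000 | 90–150 | 0.67 | within | meets |
| 20,000 | 120–200 | 0.50 | below | meets |

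**Step 3. Section 5.1 against 6.4, leaving the syringe aside**

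Take 40 mg after 10,000 IU: 40 / (10,000 / 100) = 0.4. This satisfies the 6.4 cap and breaches the lower limit in 5.1. The disagreement does not depend on how much of a syringe is injected.

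**Step 4. Initial or total heparin**

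Suppose 8,000 IU initially and 12,000 IU in total (assumed). On initial heparin the 5.1 range is 48–80 mg; on total heparin it is 72–120 mg. A dose of 100 mg is then outside the range on the first basis (1.25) and inside it on the second (0.83). The two bases coincide only if no further heparin is given.

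**The case against.** The strongest answer is that the syringe is only a container. Sections 6.5 and 7.2 say what it holds, and 7.3 gives the order of steps without saying that the whole content is injected. Leaving the amount to the operator in 6.4 would mean little if everyone received 100 mg. The 0.6–1.0 range stands just before the discretion sentence in 6.4, so discretion can be read as choice within that range. A volume also follows from the ratio and the concentration: at an assumed 10,000 IU, 60–100 mg at 10 mg/mL is 6–10 mL. An operator who does not know the content can choose that volume in either arm, so no break in blinding is shown.

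Much of this is plausible, and it makes the fixed syringe the weakest part of the point. But no section states it, and three things survive it: the lower limit is absent from the 6.4 instruction, the heparin basis is unsettled, and a single 100 mg syringe cannot reach a ratio of 0.6 above about 16,667 IU however it is used.

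A reader might go further and infer that many patients would exceed the cap. Without a heparin dose in the protocol, that has no support. Nor is the experimental treatment undefined: drug, route, ratio, concentration and timing are all stated. That dose variation would dilute or reverse the treatment effect is possible, but nothing in the document lets it be quantified.

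**Conclusion.** The point stands as an internal inconsistency in the trial-drug instructions, not as a mere lack of detail. Sections 5.1 and 6.4 differ on whether there is a lower limit, and 6.4 uses two heparin bases while 5.1 names none. Read literally, 7.3 with 7.2 gives 100 mg to all. That exceeds the 5.1 range and the 6.4 cap for any patient given less than 10,000 IU, and falls below the 5.1 lower limit above about 16,667 IU.

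The thresholds rest on the protocol's own figures and on two readings: that the whole syringe is injected, and that the cap means 1 mg per 100 IU. The number of patients affected cannot be computed. A reader might also infer that heparin and injected volume will go unrecorded, since 7.3 asks only that the need for syringe B be documented. The data lists in 7.4 are expressly not exhaustive and the case report form is not available, so that does not follow.

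**What to change.** Reconcile 5.1, 6.4, 6.5, 7.2 and 7.3 into one dosing rule. Which rule is a clinical decision for the sponsor, and none is proposed here. The reconciled text should:

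1. say whether the ratio and any cap refer to initial or total heparin, and whether a lower limit applies;
2. say in 7.3 how the volume injected from syringe A, and from syringe B when requested, follows from that rule, with the same volume instruction for active and placebo syringes so that blinding is kept;
3. make sure that the prepared syringe content can satisfy the rule over the heparin doses expected;
4. confirm that total heparin and the volume injected from each syringe are recorded for every patient, so that the delivered ratio can be reported by arm.

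The cost is a protocol clarification and, if the fields are not already there, two or three entries on the study form.
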